Maximum follow-up duration per subject will be 12 months. Primary endpoints will be evaluated at 6 months. Individual components of the primary endpoints along with the descriptive endpoints will be evaluated at 12 months.

Clinical Investigational Plan

Study Synopsis

Statistical Considerations	
Primary Efficacy Endpoint Analysis – Reduction of Bleeding: The rate of non-surgical bleeding at 6 months will be compared between the Treatment and Control Arms utilizing the Fisher’s Exact Test. The primary endpoint for efficacy will be assumed to be met if the p-value < 0.05. The assumption is that there will be a 15% rate reduction at 6 months.
 
A sample size of 330 subjects (165 in each arm) with an alpha of 0.05 will provide 80% power to demonstrate a significant difference between the Treatment and Control Arms.
 
Primary Safety Endpoint Analysis – Non-Inferiority of Stroke and Thrombus: The difference in the rates of the composite endpoint of stroke and pump thrombosis between Treatment and Control Arms and the 95% confidence limit of the difference will be evaluated. If the upper confidence limit of the difference is < 10% then the non-inferiority criterion will be considered to have been met.
 
A sample size of 338 subjects (169 in each arm) will provide 80% power, with a target alpha of 0.025 (because this will be a one-sided test on the upper confidence limit) to demonstrate non-inferiority of the Treatment Arm to the Control Arm.
 
A total study sample size of 350 subjects will provide enough statistical power to demonstrate both efficacy and safety of the warfarin only anticoagulation regimen in these patients.
 
Both primary endpoints must be met for the study to be successful.
 
Intermediate Safety Assessment: A safety assessment will be performed after 60 subjects have completed 3 months of follow-up. Both incidence of stroke and pump thrombosis will be analyzed and results will be presented to the Steering Committee. Additionally, after the initial 3-month safety review, an analysis of AEs associated with primary endpoints will be presented to the Steering Committee for continued safety assessment in regular 6-month intervals. The Steering Committee will review the findings and make a decision to proceed or stop the study due to safety concerns.

Devices Used	HM II Left Ventricular Assist Device (LVAD)

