5.3.3 RESEARCH DRUG DISPENSING

Initial dispensing of the research drug will occur after randomization, which will be performed immediately after the patient has been successfully implanted with the HM II. Resupply dispensing will occur at Month 3, Month 6, and Month 9 follow-up visits. Dispensing will be controlled at the sites with the use of ALMAC Clinical Services' WebEZ system. At each dispensing time point, the designated site personnel will log on to the WebEZ system, enter information required for randomization or resupply, and requisition a bottle to dispense to the subject from the on-site stock.

Each bottle of research drug will be tracked by bottle number. The WebEZ system will provide sites with the bottle number to be dispensed to a given subject. Site supply and resupply shipments will be automatically controlled by ALMAC Clinical Services.

If a subject reports a lost or empty bottle of research drug or is unable to attend a resupply visit, the designated site personnel will log onto the WebEZ system to requisition a replacement bottle from the onsite supply. The replacement bottle may be shipped overnight to the subject, or the subject may choose to retrieve the replacement bottle from the site in person.

Subjects should always be sufficiently supplied with research drug until their next resupply visit. Each bottle will contain 110 days of research drug, which is a sufficient supply for the period leading up to the subject's next visit, including the acceptable visit windows.

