5.3.4 RESEARCH DRUG DOSING

The research drug will be taken once daily by mouth. Warfarin therapy will be per SOC with a target INR of 2.0-2.5.

Clinical Investigational Plan**5.3.5 RESEARCH DRUG ACCOUNTABILITY**

To ensure research drug accountability, all empty research drug bottles and (if applicable) all unused doses will be returned to ALMAC Clinical Services by the site. Subjects will be instructed to return the research drug bottle and any unused portion of the research drug at each resupply visit.

The research drug bottles and unused portions will be shipped (at the Sponsor's expense) per country-specific Drug Return Instructions (DRI).

[figure not shown]
In the event that a site has several bottles or unused portions to return to ALMAC Clinical Services, return shipments may be combined into a batch shipment. Empty research bottles and unused doses should not be stored on site, and should be shipped to ALMAC Clinical Services within 14 days of receipt from the subject. Drug return instructions (DRI) will be provided during training.

Clinical Investigational Plan

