6.2 STUDY ACTIVITIES AND PROCEDURES

The clinical study will be conducted in accordance with the CIP. All parties participating in the implementation of the study will be qualified to perform their designated tasks by education, training, and experience. Applicable documentation will be maintained.

No study activities may begin until the site has received written Sponsor approval. Copies of written approval from the IRB and/or the relevant regulatory authorities, as well as all required regulatory documents must be received by the Sponsor before approval will be given.

Table 1 – Schedule of Assessments

Assessment	Baseline	Implant	Week 1 (± 3 days)	Month 1 ¹ (± 7 days)	Month 3 ¹ (± 20 days)	Month 6 ¹ (± 20 days)	Month 9 ¹ (± 20 Days)	Month 12 ¹ (± 20 days)	As Occurs/ Unscheduled
Inclusion/ Exclusion	X								
Informed Consent	X								
Demographics	X								
General and Cardiac Medical History	X								
Coagulation Assessment	X ²								
Right Heart Catheterization	X ²								X ⁴
Vital Signs	X		X	X	X	X	X	X	
Laboratory Assessments	X ³		X	X	X	X	X	X	X ⁴
Anticoagulation/Antiplatelet Medications Log	X	X	X	X	X	X	X	X	X
Echocardiogram	X ²		X ⁴	X ⁴	X ⁴	X ⁴	X ⁴	X ⁴	X ⁵
Other Medications	X			X	X	X	X	X	
ASA Resistance Testing	X								
Implant Data		X							X ⁶
Enrollment		X ⁷							
Randomization		X							
Adherence to Recommended Practices		X	X	X	X	X	X	X	
Pump Parameters		X	X	X	X	X	X	X	X ⁵
Bottle Assignment via WebEZ		X			X	X	X		
Research Drug Bottle Dispensing and Dispensing Log		X			X	X	X		X
Bridging Therapy Log		X	X						X ⁸
Anti-Factor Xa Assay Log		X	X						X ⁸
Initial Discharge Data									X
Subject Status			X	X	X	X	X	X	
Cardiac Arrhythmias			X	X	X	X	X	X	
INR & LDH Log			X	X	X	X	X	X	X
Chest/Abdominal X-Ray				X ⁹					X ⁵
Return Bottle with Remaining Test Drug to ALMAC Clinical for Accountability					X	X	X	X	
Death									X
Withdrawal (early termination)									X
Rehospitalizations			X	X	X	X	X	X	X
Adverse Events			X	X	X	X	X	X	X
Operative Procedures			X	X	X	X	X	X	X

¹ For follow-up visit scheduling, one month = 30 days.

² Most recent results within 30 days prior to implant, if collected as SOC.

³ Most recent results obtained within 30 days prior to implant will be permitted as baseline data.

⁴ If performed as SOC.

⁵ At time of suspected thrombotic adverse event or pump exchange, if performed as SOC.

⁶ Pump Exchange data collection includes: Implant Data and Recommended Practices.

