6.6 SCHEDULED FOLLOW-UP VISITS

The required assessments, follow-up schedule, and associated visit windows are generally aligned with INTERMACS, a national MCS registry. All follow-up visits are based on the initial implant date, even if a pump exchange occurs while the subject is being followed on the study. The windows for each follow-up visit are as follows:

Table 4 – Follow-Up Visit Windows

Baseline	Implant	Visit 1	Visit 2	¹ Visit 3	¹ Visit 4	¹ Visit 5	¹ Visit 6
-	-	Week 1 ± 3 days	Month 1 ± 7 days	Month 3 ± 20 days	Month 6 ± 20 days	Month 9 ± 20 days	Month 12 ± 20 days

¹ Note that the window for these visits have been shortened to ± 20 days from the original INTERMACS ± 30 days window.

The follow-up visit must occur within the designated window. Follow-up assessments for a single visit do not have to occur on the same date, but must occur within the designated window, or will be considered a CIP deviation. The Sponsor understands that some lab results may be received several days after the visit has occurred.

At the completion of the Month 12 visit, the subject has completed the study. With the exception of some lab results that may be received after the visit has occurred, no other assessments or study related activities may be performed after the final visit has occurred, even if later assessments are performed within the acceptable window. Month 12 assessments not collected by the date of the final visit will be considered a protocol deviation.

Clinical Investigational Plan

Table 5 – Scheduled Follow-Up Visit Data Collection

Study Activity	Definition
Subject Status	Initial discharge status, and visit completion
Vital Signs	Weight, blood pressure and method of blood pressure measurement
Pump Parameters	Pump Speed, Pump Flow, Pulsatility Index, and Pump Power
Cardiac Arrhythmias	Atrial (fibrillation/flutter), ventricular (fibrillation/VT), and treatment
Anticoagulation / Antiplatelet Medications	All changes made during the follow-up period All new medications started, or current medications stopped during the follow-up period must be recorded. All dose changes (including IV titrations) during the follow-up period must be recorded with the exclusion of Warfarin/Coumadin. Only the start and stop dates will be collected for Warfarin/Coumadin

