Other Medications	ACE inhibitors, inotropes, ARBs, beta blockers, antiarrhythmics, statins, nitrates, allopurinol, aldosterone blockers, antibiotics, diuretics, insulin and antidiabetic medications, and other cardiovascular medications
Bottle Dispensing	All bottles dispensed during the follow-up period (Month 3, 6 and 9 follow-up visits only), including replacement bottles that are dispensed outside of the follow-up schedule,
Bottle and Unused Research Drug Return	Bottle status and shipping information. All bottles and unused doses must be returned to ALMAC Clinical upon receipt from subject.
Laboratory Assessments	Hemoglobin (Hgb), Hematocrit (Hct), White Blood Cell Count (WBC), Platelets (PLT), Creatinine (Cr), Estimated Glomerular Filtration Rate (eGFR), LDH and INR. For diabetic patients: HbA1c, and fasting glucose Collected only if SOC: Activated Partial Thromboplastin Time (aPTT), Partial Thromboplastin Time (PTT), Plasma free Hgb (PHgb), liver function tests (AST, ALT, total bilirubin, albumin, pre-albumin), blood urea nitrogen (BUN), D-Dimers, P Selectin, fibrinogen, and Anti Factor Xa Assay (Heparin Assay). Note: To protect blinding of the study, platelet function testing (including ASA resistance testing) should be avoided during the course of the study except where indicated by the CIP.
Adherence to PREVENT Recommended Practices	Blood pressure management, INR goals, and pump speed management
Chest/Abdominal X-Ray	PA and lateral chest/abdominal X-rays (that show the entire pump relative to major cardiac/anatomical structures) will be submitted to Sponsor for independent analysis of pump position Note: Collected between Implant and Month 1 visits, or at pump thrombosis or pump exchange events
¹ Echocardiogram	LVEF, LVEDD, LVESD, AI, MR, TR, PR, including severity and/or grade, and presence of LV or LA thrombus, and aortic valve opening ratio, including percent AV area opening, and AV opening time

¹ If collected per SOC.

Clinical Investigational Plan**6.7 UNSCHEDULED VISITS****6.7.1 OPERATIVE PROCEDURES**

Data related to any cardiac or non-cardiac operative procedures occurring after enrollment will be collected. Operative procedures must be reported to the Sponsor through the EDC system immediately upon discovery of the event or, at the latest, if the operation is unknown to the implanting site (i.e. at another facility), during the next follow-up visit.

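### The 110-day bottle in Section 5.3.3 allows for one visit window, but three of the four dispensing intervals can last 130 days with both visits in window

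*Combined protocol and SAP*

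**What the plan says.** Section 5.3.3 sets the supply rule and then says how it is met. The rule is "Subjects should always be sufficiently supplied with research drug until their next resupply visit". The next sentence begins "Each bottle will contain 110 days of research drug, which is a sufficient supply for the period leading up to" and ends by naming the next visit and including the permitted windows. Drug is first dispensed after randomization, shortly after implant, and again at Months 3, 6 and 9. Section 5.3.4 sets one dose a day.

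The visit calendar is in Section 6. Table 1, note 1, says "For follow-up visit scheduling, one month = 30 days". Section 6.6 dates all follow-up visits from the initial implant, and the note to Table 4 says of Months 3 to 12: "Note that the window for these visits have been shortened to ± 20 days from the original INTERMACS ± 30 days window".

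On leftover drug, Section 5.3.5 says "Subjects will be instructed to return the research drug bottle and any unused portion of the research drug at each resupply visit".

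Section 5.3.3 also has a replacement route. It opens "If a subject reports a lost or empty bottle of research drug or is unable to attend a resupply visit", and the site may then requisition a bottle from its own stock, to be shipped overnight or collected. Table 5 expects this, since dispensing records are to cover all bottles, "including replacement bottles that are dispensed outside of the follow-up schedule".

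**The concern.** Because every visit is dated from implant and not from the visit before it, the windows at the two ends of an interval add. The figure of 110 days appears to allow for only one of them. If so, a site can follow the protocol exactly, keep every visit in window, and still send a subject home with too few doses.

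In the Control Arm a gap in supply is a gap in aspirin, and no visit deviation would flag it. The sufficiency sentence also tells site staff that no check is needed, which removes the reason to look ahead when a visit is booked late.

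The outcomes at risk are the later ones. The Synopsis says "Individual components of the primary endpoints along with the descriptive endpoints will be evaluated at 12 months", and the descriptive endpoints include an as-treated analysis of antiplatelet medication.

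**Working it through.** **Inputs**
- Bottle: 110 doses (5.3.3), taken once daily (5.3.4).
- Month: 30 days (Table 1, note 1), so visits are targeted at Days 90, 180, 270 and 360.
- Window: ±20 days at Months 3, 6, 9 and 12 (Table 4). Implant has no window.
- Anchor: initial implant date (6.6).
- Carry-over of unused doses: none (5.3.5).

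**Reproducing the plan's figure**

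3 × 30 + 20 = 110. This is a nominal 90-day interval plus the late window of the next visit only.

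**Longest interval with both visits in window**

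Maximum = (target of next visit + its window) − (target of current visit − its window).

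| Interval | Calculation | Longest | Shortfall of one bottle |
|---|---|---|---|
| Implant to Month 3 | (90 + 20) − 0 | 110 days | 0 |
| Month 3 to 6 | (180 + 20) − (90 − 20) = 200 − 70 | 130 days | 20 doses |
| Month 6 to 9 | (270 + 20) − (180 − 20) = 290 − 160 | 130 days | 20 doses |
| Month 9 to 12 | (360 + 20) − (270 − 20) = 380 − 250 | 130 days | 20 doses |

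Section 4.10 counts the implant date as Day 1. That moves all visit dates equally and leaves the last three intervals unchanged.

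**When a shortfall occurs.** The nominal interval is 90 days, so the next visit must slip by more than 20 days relative to the one before it. Any pair of visits 110 days apart or less is covered.

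**How many intervals in one subject.** Two adjacent intervals together last at most 180 + 20 + 20 = 220 days, so they cannot both exceed 110. At most two of the three can run long in the same subject: Months 3-6 and 9-12, with Month 3 early, Month 6 late, Month 9 early and Month 12 late.

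**Would leftovers cover it?** If they were kept, yes: cumulative supply of 220, 330 and 440 doses exceeds the latest visit days of 200, 290 and 380. The return rule in 5.3.5 rules this out.

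**Earliest run-out.** Day 70 + 110 = Day 180.

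**How often.** The documents do not say how visits will spread within the windows. As an illustration only, assume that visit shifts are independent and uniform on whole days from −w to +w:
- w = 10: the largest relative slip is 20 days, so 0% of intervals exceed 110 days.
- w = 15: 55 of 31² = 961 combinations, or 5.7%; mean shortfall when short, 220/55 = 4.0 doses.
- w = 20: 210 of 41² = 1,681 combinations, or 12.5%; mean shortfall when short, 1,540/210 = 7.3 doses.

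All three are per interval and before any replacement bottle.

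**The case against.** The arithmetic is not in dispute. The case on the other side is that the consequence is small and safeguards exist.

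- *The duty to keep subjects supplied is already written.* It is, and it looks forward. But the sentence right after it says that one bottle meets the duty, which is wrong. What is missing is a working trigger, not the obligation.
- *The replacement route would limit the loss.* This largely stands. Stock is on site, overnight shipping is allowed, and Table 1 marks dispensing as an as-needed activity. A subject who reports promptly might lose about a day, so 20 doses is a ceiling for one bottle and not expected time off drug. Still, a subject booked late but in window is not unable to attend, and Month 12 is not a resupply visit. In those cases the remaining trigger is an empty bottle, reported once the doses are gone.
- *Separate site documents may cover this.* The WebEZ instructions are not available here, so the point is limited to what the protocol text says.
- *The primary result is safe.* Agreed. Success depends on the two 6-month endpoints, and the earliest run-out is Day 180. Medication changes are also logged.
- *The frequency is unknown.* Agreed. The 12.5% needs visits spread evenly over the full window, for which the documents give no basis, and 0% is within the range.
- *In Months 9-12 the supply rule is not breached, because it runs to the next resupply visit.* Correct on its wording. The sufficiency sentence, which refers to the next visit, is still wrong there, and Section 12.2 keeps subjects on research drug for the whole study.
- *Rewording alone would be enough.* It would make the text true, but sites would still be left to react to an empty bottle.

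**Conclusion.** The sufficiency sentence in Section 5.3.3 is wrong as written. It holds for implant to Month 3, where the maximum is exactly 110 days. It fails for the three later intervals, each of which can reach 130 days in window, leaving one bottle up to 20 doses short. This follows from the protocol's own month length, windows, visit anchor and return rule, with no outside assumption.

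The practical consequence is minor. Time off drug arises only if one visit is early enough and the next late enough, and a replacement does not then arrive in time. The 6-month primary endpoints are not materially affected. What is exposed is treatment adherence behind the 12-month component and descriptive endpoints. The only estimates of frequency (0% to 12.5% of these intervals) rest on an assumed uniform spread of visits and should not be read as forecasts.

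**What to change.** Replace the sufficiency sentence in Section 5.3.3 and add one rule, for example:

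> Each bottle holds 110 daily doses. At Months 3, 6 and 9, if the next visit is booked, or later rebooked, for more than 110 days after dispensing, the site dispenses a second bottle at that visit or ships one before the first runs out.

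The bottle size, the visit windows and the return rule in Section 5.3.5 can stay as they are. The cost is two sentences and a site training note, with slightly more drug supply and accountability work. The drug vendor would need to confirm that WebEZ lets a site requisition a second bottle before the first is reported empty.

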5.3.4 RESEARCH DRUG DOSING

The research drug will be taken once daily by mouth. Warfarin therapy will be per SOC with a target INR of 2.0-2.5.

Clinical Investigational Plan**5.3.5 RESEARCH DRUG ACCOUNTABILITY**

To ensure research drug accountability, all empty research drug bottles and (if applicable) all unused doses will be returned to ALMAC Clinical Services by the site. Subjects will be instructed to return the research drug bottle and any unused portion of the research drug at each resupply visit.

The research drug bottles and unused portions will be shipped (at the Sponsor's expense) per country-specific Drug Return Instructions (DRI).

[figure not shown]
In the event that a site has several bottles or unused portions to return to ALMAC Clinical Services, return shipments may be combined into a batch shipment. Empty research bottles and unused doses should not be stored on site, and should be shipped to ALMAC Clinical Services within 14 days of receipt from the subject. Drug return instructions (DRI) will be provided during training.

Clinical Investigational Plan

6 PROCEDURES

6.1 STUDY FLOW CHART

Figure 2 – Study Overview

Clinical Investigational Plan

6.2 STUDY ACTIVITIES AND PROCEDURES

The clinical study will be conducted in accordance with the CIP. All parties participating in the implementation of the study will be qualified to perform their designated tasks by education, training, and experience. Applicable documentation will be maintained.

No study activities may begin until the site has received written Sponsor approval. Copies of written approval from the IRB and/or the relevant regulatory authorities, as well as all required regulatory documents must be received by the Sponsor before approval will be given.

Table 1 – Schedule of Assessments

Assessment	Baseline	Implant	Week 1 (± 3 days)	Month 1 ¹ (± 7 days)	Month 3 ¹ (± 20 days)	Month 6 ¹ (± 20 days)	Month 9 ¹ (± 20 Days)	Month 12 ¹ (± 20 days)	As Occurs/ Unscheduled
Inclusion/ Exclusion	X								
Informed Consent	X								
Demographics	X								
General and Cardiac Medical History	X								
Coagulation Assessment	X ²								
Right Heart Catheterization	X ²								X ⁴
Vital Signs	X		X	X	X	X	X	X	
Laboratory Assessments	X ³		X	X	X	X	X	X	X ⁴
Anticoagulation/Antiplatelet Medications Log	X	X	X	X	X	X	X	X	X
Echocardiogram	X ²		X ⁴	X ⁴	X ⁴	X ⁴	X ⁴	X ⁴	X ⁵
Other Medications	X			X	X	X	X	X	
ASA Resistance Testing	X								
Implant Data		X							X ⁶
Enrollment		X ⁷							
Randomization		X							
Adherence to Recommended Practices		X	X	X	X	X	X	X	
Pump Parameters		X	X	X	X	X	X	X	X ⁵
Bottle Assignment via WebEZ		X			X	X	X		
Research Drug Bottle Dispensing and Dispensing Log		X			X	X	X		X
Bridging Therapy Log		X	X						X ⁸
Anti-Factor Xa Assay Log		X	X						X ⁸
Initial Discharge Data									X
Subject Status			X	X	X	X	X	X	
Cardiac Arrhythmias			X	X	X	X	X	X	
INR & LDH Log			X	X	X	X	X	X	X
Chest/Abdominal X-Ray				X ⁹					X ⁵
Return Bottle with Remaining Test Drug to ALMAC Clinical for Accountability					X	X	X	X	
Death									X
Withdrawal (early termination)									X
Rehospitalizations			X	X	X	X	X	X	X
Adverse Events			X	X	X	X	X	X	X
Operative Procedures			X	X	X	X	X	X	X

¹ For follow-up visit scheduling, one month = 30 days.

² Most recent results within 30 days prior to implant, if collected as SOC.

³ Most recent results obtained within 30 days prior to implant will be permitted as baseline data.

⁴ If performed as SOC.

⁵ At time of suspected thrombotic adverse event or pump exchange, if performed as SOC.

⁶ Pump Exchange data collection includes: Implant Data and Recommended Practices.

⁷ Subject is considered enrolled when inclusion/exclusion criteria are met; has been successfully implanted with a HM II LVAD; and has been randomized to a research drug arm (Treatment or Control).

⁸ Within the first 21 days post implant.

⁹ Best view available between Implant and Month 1 visit.

Clinical Investigational Plan**6.2.1 ANTIPLATELET TESTING AND PLATELET FUNCTION TESTING**

Subjects in both the Treatment and Control Arms will receive ASA resistance testing (e.g. TEG® PlateletMapping®, VerifyNow®, etc.) at the baseline visit. After obtaining informed consent, testing will be performed prior to implantation, and may require a brief administration of ASA (recommended 3-5 days) to subjects who are not currently on ASA therapy. Testing should be timed adequately prior to surgery so as not to effect subjects' ability to reach post-operative hemodynamic stability.

To retain investigator and patient blinding to the test results, all site labs should be directed to return de-identified (patient screening ID only) ASA resistance test results at the Sponsor's expense to the Sponsor. Results will not be entered into the subject's hospital record to protect blinding.

While the subject is on the research drug, antiplatelet testing or platelet function testing should not be performed, as it may result in un-blinding of the subject or the investigator. Un-blinding of the subject or investigator will be considered a CIP deviation and the subject will be withdrawn from the study.

